ECGs before and 1 & 4 hr post dose		X					^e DXA total body scans at 2, 6, &12 mo; spine and non-dominant hip scans at 12 mo (screening scans will serve as baseline)
Diet assessment ^a		X				X	^f Serum P1NP at 0, 2, 6, and 12 mo; serum IGF-1 and CTX at 0 and 12 mo; serum 25(OH)D at 0 and mo 6; and alpha-acid glycoprotein at visit 0; archive 4 aliquots serum and 1 of plasma at 0 and 12 mo.
Questionnaires ^b		X		X		X	^g Safety monitoring: fasting plasma glucose & serum AST/ALT at 0, 2, 6, and 12 mo; symptoms and other AEs documented
Muscle strength ^c	X	X	X	X		X	^h By pill diary and counting returned pills
Muscle perform. ^d		X	X	X		X	ⁱ Administer 60-mg oral dose of D ₃ -creatine
DXA scans ^e			X	X		X	^j Collect fasting spot urine for D ₃ -creatine dilution determination
Study blood ^f		X	X	X		X	
Dispense pills		X	X	X			
Safety measures ^g		X	X	X		X	
Adherence ^h			X	X		X	
D ₃ -creatine dosing ⁱ	X				X		
Fasting spot urine ^j		X				X	
Waist circumference						X	

In addition to the above study visits, we will contact participants by telephone at 4, 8, and 10 months to determine whether they have any study related concerns and to remind them of the importance of taking one study pill per day. The content of these calls will be documented on the Call/comment Log.

C. Inclusion and exclusion criteria

Inclusion criteria: Ability to sign informed consent form; community dwelling men (who are sterile or agree to use contraception throughout the study) and postmenopausal women (no menses for 5 years; early postmenopausal women are ineligible because their bone turnover rate is changing rapidly); age 50 years and older; sarcopenia defined as maximum grip strength <35.5 kg (men) and <20 kg (women) in either hand (excluding hands with severe pain or recent surgery) and/or gait speed <0.8 m/sec (11); osteopenia defined as spine (at L1, L2, L3, or L4) or non-dominant total hip or femoral neck BMD T-score between -1.0 and -2.5; mini-mental state examination (MMSE) score >21.

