Total body muscle mass will be assessed directly by the D₃-creatine dilution method (27). Low muscle mass measured by this method has been associated with slower walking speed, lower SPPB score, and more falls in older men (27). The D₃-creatine dilution method involves a participant ingesting a capsule containing the 60-mg dose of stable isotope-labeled creatine (D₃-creatine), and then providing a fasting morning urine sample 72–144 hours (3–6 days) later. To minimize variability in this muscle mass measurement, participants will be asked not to eat foods containing creatine or creatinine (animal products) after their mid-day meal on the day prior to these urine collections on visits 0 and 12 months. A handout will be provided to guide participants in what they should and should not eat on these two occasions. Urine D₃-creatinine, unlabeled creatinine, and creatine are measured using high performance liquid chromatography and tandem mass spectroscopy; these measures are then included in an algorithm to determine total body creatine pool size and thus skeletal muscle mass (39). The doses will be prepared by Greenpark Pharmaceuticals in Houston, TX. The urine samples will be de-identified and sent to [name] laboratory at U.C. Berkeley for analysis. [name] will be blinded to treatment group and sequence (baseline, 12 mo) during the analyses.

Biochemical measurements

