Research material will include records made of the response to prescreening questionnaires, medical history, height, weight, blood pressure, and DXA scans on the screening visit. During the study, additional data in the form of records from study visits, responses to questionnaires and testing procedures will be obtained as described above.

b. Known potential risks to subjects

Anamorelin has the potential to cause hyperglycemia. In the two Phase 3 trials, hyperglycemia grade 1-2 (requiring treatment with diet modification or an oral agent) occurred in 5% (vs 3% in placebo) in one trial and 3% (vs <1% in placebo) in the other trial (26). Grade 3 hyperglycemia (requiring insulin) occurred in ≤ 1% of anamorelin and placebo users in both trials. Patients with uncontrolled diabetes (defined as fasting glucose ≥200 mg/dl) were excluded from participating in the published Phase 3 trials. In the 12-wk safety extension period, the incidence of drug-related AEs declined (29). Hyperglycemia occurred in 1.2% in the anamorelin group compared with none in the placebo group.

Anamorelin has the potential to cause gastrointestinal symptoms. In the two 12-wk Phase 3 trials, mild to moderate gastrointestinal complaints occurred in 6% (vs 2% in placebo) in one trial and 2% (versus <1% in placebo) in the other (26). Of the gastrointestinal complaints, nausea accounted for half to two thirds of the complaints, constipation one quarter, and vomiting 0 to one quarter. In one of the trials there were no severe gastrointestinal adverse events and in the other, severe nausea and vomiting occurred in <1% (26). In the 12-wk safety extension, nausea occurred in 0.6% of the anamorelin group, compared with 0 in the placebo group, indicating that anamorelin is suitable for long-term use (29). The risk of gastrointestinal symptoms occurring in our study subjects may be lower than in the stage 4 lung cancer patients who were often also receiving cancer treatments, but this is unknown.

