DXA scans will be performed by DXA technicians who are experienced and certified by International Society for Clinical Densitometry and the State of MA. Should a participant's BMD of the spine or hip decline by >7% on 2 consecutive measurements, the participant will be notified and referred to his/her PCP. The participant will remain in the study.

The muscle performance measurements will be administered by an experienced research coordinator who will observe the subject during testing.

Because of the potential of anamorelin to increase fasting plasma glucose, we will monitor glucose on each visit. If it is elevated (≥ 200 mg/dl), we will repeat the measurement. If again elevated ≥ 200 mg/dl, the study pills will be discontinued. Discontinuation of study pills will be managed without unblinding the study team, and those participants will continue with study measurements (for the intent-to-treat analysis). Subjects will be asked to consume their usual dinner on the evening prior to each study visit.

Sporadic, mild increases in serum AST/ALT have been observed in subjects on anamorelin. We will monitor AST/ALT on each study visit and discontinue use of anamorelin if these levels exceed 2x the upper end of the reference range (>74 and >68 MU/ml, respectively) on repeat measurement.

In order for participants to achieve therapeutic levels of anamorelin, we will exclude subjects on CYP3A4 inducers which may increase the metabolism of anamorelin (e.g., rifampin). We will also have participants take study pills 1 hour before breakfast, as food reduces anamorelin bioavailability.

To minimize risk that anamorelin levels become supra-therapeutic, we will: a) instruct participants never to take more than one study pill per day (that is, not to 'catch up' after missing a dose); b) exclude participants taking strong CYP3A4 inhibitors (ketoconazole, clarithromycin, itraconazole, nefazodone, telithromycin); c) exclude participants taking drugs with high binding affinity to AAG because they have the potential to displace anamorelin from binding (e.g., carvedilol, chlorpromazine); d) exclude participants taking inhibitors of P-glycoprotein (e.g., verapamil, quinidine), and e) inhibitors of OATP1B3 (e.g., cyclosporine, rifampicin)

We will instruct participants to notify [name] of any new prescriptions (before taking the first dose) and of any changes in health status or of any hospitalizations or emergency room visits.

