Nonclinical data indicate that the T_{max} in cardiac tissue is delayed compared with plasma T_{max} (4 hrs vs 1 hr, respectively). We will perform a screening ECG and exclude individuals with clinically meaningful abnormalities. We will also perform ECGs before and 1 and 4 hrs after the first dose of the study pills.

Stopping rules

- We will discontinue the subject's participation in the study if the QT interval exceeds 470 ms or if other clinically meaningful ECG changes occur at either 1 hr or 4-hrs post first dose (4 hrs post dose is the time when the anamorelin concentration in cardiac tissue is maximal).
- We will discontinue the subject's participation in the study in the event that he/she develops cardiac symptoms (e.g., chest pain, chest pressure, palpitations) or evidence of significant fluid retention (peripheral edema, pulmonary congestion).
- We will discontinue a subject's participation in the study if he/she is prescribed the following drugs during the study:
 - CYP3A4 inhibitor (ketoconazole, clarithromycin, itraconazole, nefazodone, or telithromycin)
 - Channel blocking antiarrhythmic medication (flecainide, procainamide, propafenone, quinidine)
 - Drugs with high affinity to AAG (carvedilol, chlorpromazine)
 - Inhibitors of P-glycoprotein (verapamil, quinidine)
 - Inhibitors of OATP1B3 (cyclosporine, rifampicin)
- We will discontinue a subject's participation in the study if he/she develops glycemia defined as fasting plasma glucose ≥ 200 mg/dl on two consecutive measures.

Subjects developing these findings or symptoms will be referred to their physicians and these adverse events will be recorded and reported to the IRB, the NIH, and Helsinn Therapeutics. The study physician will follow up with the subject and his/her physician until symptoms have been appropriately addressed.

We will exclude subjects with eGFR < 30 ml/min.

The study will be approved by the Tufts IRB before anyone will be recruited for the study. All study personnel have been certified by the Tufts IRB to work with clinical research participants. All research activity will take place at the HNRCA. Written informed consent will be obtained from each participant.

The PI will inform the IRB of any updated information that may affect the conduct of this study or subject safety, rights, welfare or willingness to take part in the research.

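### Two passages give incompatible instructions for a confirmed fasting glucose of 200 mg/dl or more: one stops the pills and keeps measuring, the other ends participation

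*Combined protocol and SAP*

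**What the plan says.** Protection against risks sets out a glucose rule. A fasting value of 200 mg/dl or more is repeated, and then "If again elevated ≥ 200 mg/dl, the study pills will be discontinued". The blind is kept, and "those participants will continue with study measurements (for the intent-to-treat analysis").

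The Stopping rules list, a little further on, says that the team will "discontinue a subject's participation in the study if he/she develops glycemia defined as fasting plasma glucose ≥ 200 mg/dl on two consecutive measures". After that it provides for referral, adverse event reporting and medical follow-up, but not for study visits.

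Other relevant text:

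- Section K (Withdrawal from the study) allows a participant to be off pills and still attend visits. It limits permanent off-study status to withdrawal of consent, then adds that the principal investigator may withdraw someone for safety.
- The footnotes to the Schedule of activities place safety monitoring, "fasting plasma glucose & serum AST/ALT at 0, 2, 6, and 12 mo".
- The D₃-creatine section refers to "urine collections on visits 0 and 12 months", and the schedule shows no other D₃-creatine measurement.
- Section J (Data analysis) compares 12-month change with a two-sample t-test. It gives no method for missing values, and its intention-to-treat population is everyone with at least one visit beyond baseline.

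**The concern.** The trigger is the same in both places and the consequences exclude each other. Whichever instruction staff follow, they depart from the other.

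The choice matters because the primary endpoint has a single follow-up measurement. If participation ends at month 2 or month 6, that measurement is never taken. The participant still belongs to the intention-to-treat population but contributes nothing to the primary comparison. Secondary data are less exposed, because P1NP and whole-body DXA are also measured at months 2 and 6, and the Withdrawal paragraph lets values obtained before withdrawal be used.

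The protocol itself links this trigger to the drug. In the two Phase 3 trials, Grade 1-2 hyperglycemia "occurred in 5% (vs 3% in placebo) in one trial and 3% (vs <1% in placebo) in the other trial". For the extension it reports: "Hyperglycemia occurred in 1.2% in the anamorelin group compared with none in the placebo group". A missing primary outcome caused by a possible drug effect is the kind of loss that continued measurement is meant to prevent.

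**Working it through.** **1. Do the two rules meet on the same event?**

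| | Protection against risks | Stopping rules |
|---|---|---|
| Trigger | Fasting glucose at or above 200 mg/dl, again on repeat | Fasting glucose at or above 200 mg/dl, two measures in a row |
| Study pills | Stopped | Stopped, because participation ends |
| Later measurements | Continue | None provided for |
| 12-month D₃-creatine | Obtained | Lost if triggered at month 2 or 6 |

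A high value followed by a high repeat satisfies both triggers. The first column agrees with Section K and with the neighbouring AST/ALT rule, which stops the drug only.

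**2. The plan's own sample size.** Inputs from Section I (Study power): SD of change 1.84 kg, difference 2.28 kg, 12 per group. Alpha of 0.05 is stated under the secondary aims; I assume that it is two-sided and applies to Aim 1. Power for Aim 1 is not stated; I assume 80%. By noncentral t, the minimal detectable difference is 2.20 kg with 12 per arm and 2.31 kg with 11, so the stated 12 reproduces. Power at 2.28 kg with 12 per arm is 82.7%.

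**3. How many events?** The documents give no rate for this trigger and do not map 200 mg/dl to a toxicity grade, so I show a range. Known potential risks to subjects gives 12-week figures in cancer patients. With 32 enrolled 1:1, there are 16 on anamorelin.

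- Grade 3, at most 1% in both arms: 16 × 0.01 = 0.16
- Extension period, 1.2%: 16 × 0.012 = 0.19
- Grade 1-2, higher of the two trials, 5%: 16 × 0.05 = 0.80

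If the 12-week rate held to week 26 (an assumption), 16 × (1 − (1 − p)^(26/12)) gives 0.34 at 1% and 1.68 at 5%. These are probably too high. The protocol says drug-related events declined in the extension. This trial excludes screening glucose above 150 mg/dl, whereas the earlier trials excluded 200 mg/dl or more.

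**4. What does one participant do to the primary comparison?** Let the on-drug effect be 2.28 kg, and let one of n anamorelin participants stop pills and keep a share r of the effect (r from 0 to 0.5, assumed). The intention-to-treat difference is 2.28 × ((n − 1) + r)/n. Dropping that participant leaves the estimate at 2.28.

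| | 16 per arm | 12 per arm |
|---|---|---|
| SE = 1.84 × √(2/n) | 0.651 kg | 0.751 kg |
| Intention-to-treat difference, r = 0 | 2.28 × 15/16 = 2.14 kg | 2.28 × 11/12 = 2.09 kg |
| Intention-to-treat difference, r = 0.5 | 2.28 × 15.5/16 = 2.21 kg | 2.28 × 11.5/12 = 2.185 kg |
| Overstatement if dropped, r = 0 to 0.5 | 0.14 to 0.07 kg | 0.19 to 0.10 kg |
| Power if kept, r = 0 to 0.5 | 88.9% to 90.7% | 75.8% to 79.4% |
| Power if lost | 91.5% (15 v 16) | 80.8% (11 v 12) |

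Keeping the participant raises power only if about 72% of the effect is retained with 16 per arm, or 71% with 12.

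**The case against.** The best defence is that the plan already leans the right way. Protection against risks names the intention-to-treat reason for continued measurement, and Section K treats being off pills as compatible with staying in the study. A sensible team would probably keep measuring. Section K also lets the principal investigator withdraw someone for safety, which gives the stopping rule some cover. But that power is discretionary, whereas the stopping rule is automatic and contradicts an explicit instruction for the same event. The cover does not reconcile them.

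It is also fair to say that the event is rare. No imbalance between arms is reported at Grade 3, the allowance of 8 losses (32 enrolled, 24 completers) may absorb any exits, and there may be none. This stands, and it limits the weight of the point.

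A reader might infer that the whole Stopping rules list is at fault, since the ECG, cardiac or fluid-retention and prescription rules ("We will discontinue a subject's participation in the study if he/she is prescribed the following drugs during the study") also end participation. The documents do not support that. No other passage contradicts those rules, safety withdrawal is permitted, and safety reasons are given for the listed drugs. Whether they could be softer is a clinical judgement. Nor does this point call for a new intention-to-treat definition: someone removed at month 2 or 6 is already in that population, and counting first-dose ECG exits would add nothing to the t-test without a 12-month value.

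**Conclusion.** The contradiction is certain, because it rests on the text alone. Its effect on the primary analysis is conditional: a value is lost only if the stopping rule is the one followed and the trigger occurs at the 2- or 6-month check.

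The expected size is small: roughly 0.16 to 0.8 anamorelin participants per 12 weeks, using rates from a different population and milder grades at the upper end. Each one lost would move the estimate by about 0.07 to 0.19 kg under the assumed retention, against a standard error of 0.65 to 0.75 kg.

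A reader might infer that the primary result will be biased, or that the trial loses power by removing these participants. Neither is shown. The quoted hyperglycemia differences are not counts of this trigger in this population, and over the retention range assumed here, removal gives slightly higher power than keeping. The reason to act is a single workable rule and an intention-to-treat comparison that includes the people the protocol says it will include.

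**What to change.** Replace the glucose bullet under Stopping rules with: *Study pills will be stopped; scheduled measurements continue, including the day 361 D₃-creatine dose and the 12-month urine, unless consent is withdrawn or the study physician judges continued participation unsafe.* Report pill stops and missing 12-month values by arm. Leave the other stopping rules and the intention-to-treat definition as they are.

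The cost is one wording amendment, with a check that the consent form agrees (it is not available here). The visits are already scheduled.

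The downside is dilution by off-drug outcomes. For one such participant it is 0.8 to 2.6 points of power with 16 per arm (91.5 − 90.7 and 91.5 − 88.9). At the planned 12 completers per arm it is 1.4 to 5.0 points (80.8 − 79.4 and 80.8 − 75.8), which takes power just below 80%. The per-protocol analysis already planned in Section J excludes selected protocol deviations, so it can address the on-drug effect if pill stops are listed among them.

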Secondary aims - With 4 measurements (baseline, 2, 6, and 12 months), we will test whether the change over time is linear with use of linear models with random effects. The observed pattern of change in ALM over time will give an indication of the potential long-term benefit (or lack thereof) of anamorelin treatment. A significance level of 0.05 will be used.

The findings from secondary (and exploratory) analyses will be used for hypothesis generation, rather than to draw conclusions.

Exploratory aims – Exploratory outcomes will be analyzed as described above. For those with more than two measurements, the pattern of change will be analyzed as described above for ALM.

The primary analyses will follow intention-to-treat principles. The intent to treat population will include all subjects who had 1 or more visits after visit 0 (baseline). We will also perform per protocol analyses, in which subjects who develop clinical conditions during the study that influence the study outcomes (i.e., started treatment on an osteoporosis drug or glucocorticoids) or with selected protocol deviations will be excluded. Data will be diagnosed to evaluate validity of model assumptions. Assumptions of normality and homoscedasticity will be evaluated in these models and appropriate variable transformations will be applied if needed to satisfy model assumptions. If model assumptions do not hold for the linear mixed models, robust standard errors will be used. An exploratory per-protocol analysis will also be performed.

Safety and tolerability measures will be summarized for each treatment group based on clinical symptoms and circulating levels of glucose and ALT/AST. Adherence will be assessed by intake diary and pill counts.

K. Withdrawal from the study

Participants can go permanently “off study” only for withdrawal of consent, defined as no longer wishing to participate in all aspects of the trial. The PI may also withdraw participants for safety reasons. Participants can be off of study pills (non-adherent) but remain in the study and return for scheduled follow-up visits. Participants who are instructed by their doctor to gain weight during the study will not be withdrawn from the study.

PROTECTION OF HUMAN SUBJECTS

a. Materials and potential risks

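### A confirmed fasting glucose of 200 mg/dl or more stops the pills but not follow-up in one section and ends participation in another; probably zero or one primary value is at stake

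*Combined protocol and SAP*

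**What the plan says.** Four places in the combined protocol and SAP bear on this.

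- **Protection against risks.** Glucose is monitored at each visit. A value of 200 mg/dl or more is repeated, and if the repeat is also at or above 200 the study pills are stopped without unblinding the team. Follow-up then goes on: "those participants will continue with study measurements (for the intent-to-treat analysis").
- **Stopping rules.** The glucose bullet says that the team will discontinue a subject's "participation in the study if he/she develops glycemia defined as fasting plasma glucose ≥ 200 mg/dl on two consecutive measures".
- **Section K, Withdrawal from the study.** Permanent off-study status is "only for withdrawal of consent, defined as no longer wishing to participate in all aspects of the trial". Stopping treatment is kept separate from leaving: "Participants can be off of study pills (non-adherent) but remain in the study and return for scheduled follow-up visits". The same paragraph adds: "The PI may also withdraw participants for safety reasons".
- **Section J, Data analysis.** The primary analysis follows intention to treat. "The intent to treat population will include all subjects who had 1 or more visits after visit 0 (baseline"). The primary test is a two-sample t-test on the 12-month change in muscle mass.

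The schedule of activities places the D₃-creatine dose and urine only around baseline and month 12. After baseline, glucose is checked at 2, 6 and 12 months.

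**The concern.** The two glucose instructions share a trigger. A value that is at or above 200 mg/dl and again at or above 200 on repeat is also two consecutive measures at that level. Both instructions are mandatory, and each forbids what the other requires. Handling any such event therefore breaches one of them, and staff would have to choose case by case.

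The choice decides whether the primary value exists. A participant taken out at month 2 or 6 has attended a visit after baseline and so belongs to the intention-to-treat population, but never reaches the second D₃-creatine measurement. The t-test on change cannot use that person, and section J names no substitute for a missing primary value. A stop first triggered at the 12-month check need cost nothing.

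The loss may also be informative. The protocol itself names raised glucose as a potential effect of anamorelin, so removal on this ground need not be random with respect to treatment or muscle response.

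**Working it through.** **1. Do the texts conflict?**

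| | Protection against risks | Stopping rules |
|---|---|---|
| Trigger | fasting glucose ≥200 mg/dl, confirmed on repeat | fasting glucose ≥200 mg/dl, two consecutive measures |
| Study pills | stopped | stopped, because participation ends |
| Study measurements | continue | end |
| Stated reason | the intention-to-treat analysis | none given |

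The drug stops at the same threshold either way. Only data retention differs. Section K treats being off pills and being off study as different states, so the two instructions cannot be read as synonyms.

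**2. The plan's own sample size.** Inputs from section I: SD of change 1.84 kg, target difference 2.28 kg, 12 per group. Assumed for the primary test, because section I does not state them: two-sided 0.05 and 80% power. With the noncentral t:

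- 12 vs 12: SE = 1.84 × √(1/12 + 1/12) = 0.751; noncentrality = 2.28/0.751 = 3.04 on 22 df; power 82.7%. The difference detectable with 80% power is 2.20 kg, below 2.28 kg as the plan says.
- 11 vs 11: detectable difference 2.31 kg, so 12 is the smallest equal group size that works. The plan's figure reproduces.

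**3. How many primary values could be lost?** The documents give no rate for a confirmed fasting glucose of 200 mg/dl or more. The nearest proxies, in Known potential risks to subjects, each cover 12 weeks:

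- Main trials: "Grade 3 hyperglycemia (requiring insulin) occurred in ≤ 1% of anamorelin and placebo users in both trials".
- Extension: "Hyperglycemia occurred in 1.2% in the anamorelin group compared with none in the placebo group".

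Assumptions: 16 participants per arm (32 enrolled 1:1). Each 12-week rate p is taken as given, or compounded over four periods as 1 − (1 − p)⁴, which gives 3.94% for 1% and 4.71% for 1.2%. A share f = 2/3 of stops falls at month 2 or 6 (an even split over three checks). With q = f × p in each arm:

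- Expected losses = 16 × (q_A + q_P)
- P(0) = (1 − q_A)¹⁶ × (1 − q_P)¹⁶
- P(0 or 1) = P(0) × [1 + 16q_A/(1 − q_A) + 16q_P/(1 − q_P)]

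| Proxy (anamorelin / placebo) | Expected losses | P(0) | P(0 or 1) |
|---|---|---|---|
| Grade 3 as given, 1% / 1% | 0.21 | 81% | 98% |
| Grade 3 compounded, 3.94% / 3.94% | 0.84 | 43% | 79.5% |
| Extension as given, 1.2% / 0% | 0.13 | 88% | 99% |
| Extension compounded, 4.71% / 0% | 0.50 | 60% | 91% |

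A constant hazard over the unequal 2-, 4- and 6-month intervals puts half of detections at month 12. Then f = 1/2 and the least favourable row (grade 3 compounded) improves to 0.63 expected and 87%.

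Stress bound: count every grade 1-2 event as a trigger (5% vs 3%; 3% vs <1%, with <1% taken as 1%) and compound it. Expected losses at f = 2/3 are then 3.2 and 1.6, and P(0 or 1) falls to 16% and 50%.

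**4. What does one loss cost?** Planned dropout is 32 − 24 = 8, so a single glucose stop would usually fall inside that reserve. If the reserve is already used up:

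- 11 vs 12: SE = 1.84 × √(1/11 + 1/12) = 0.768; noncentrality 2.97 on 21 df; power 80.8%; detectable difference 2.26 kg, still below 2.28 kg.
- 10 vs 12 (two lost from one arm): power 78.6%; detectable difference 2.32 kg.

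On bias, dropping one of 12 values that lies k SD from its group mean moves that mean by k × 1.84/11, which is 0.17 kg for k = 1 and 0.33 kg for k = 2, against an SE of the difference of 0.75 kg.

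**The case against.** The strongest reply is that this is a minor wording matter which the documents nearly resolve. The Protection against risks text is the more detailed rule, gives its reason, and agrees with section K on off-pill follow-up. This shows what the authors probably intended, but it does not make the Stopping rules bullet harmless. Section K and the later Withdrawal paragraph both let participation be ended for safety, so staff could cite them for the opposite choice.

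A second reply is that the numbers are soft. That stands. The rates are 12-week proxies from cancer patients, the event is not the one that triggers the rule, and the timing split is assumed. Only the order of magnitude should be relied on.

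A third is that other Stopping rules bullets (ECG changes, cardiac symptoms, fluid retention, prescribed drugs) also end participation and sit uneasily with section K. That is true, but none of them is contradicted by an explicit instruction to keep measuring, and they can be read as safety withdrawals. The point is confined to glucose.

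Three stronger readings are tempting and are not supported:

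- **Losses would concentrate in the anamorelin arm and bias the result.** This is possible but not shown. The excess over placebo is in grade 1-2 events and in the extension; grade 3 is reported at ≤1% for both anamorelin and placebo users.
- **The trial would be underpowered.** One loss, even beyond the planned dropout, leaves the detectable difference below 2.28 kg.
- **Participant safety is left uncertain.** Both rules stop the drug at the same value.

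**Conclusion.** The inconsistency is real, is in current text, and is confined to the glucose bullet. No statement in the protocol says which instruction governs. If the Stopping rules wording is followed at month 2 or 6, an intention-to-treat participant loses the only post-baseline primary measurement, after an event that the protocol links to the drug.

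The effect is small. The likely number of lost primary values is zero or one, with a probability of roughly 80% to 99%, and such a loss would usually fall within the 8 planned dropouts. This rests on using the grade 3 and extension rates as proxies, taken as given or compounded to about 12 months. It fails only if milder hyperglycemia is counted as a trigger and compounded. That bound is overstated, because grade 1-2 covers events managed with diet or an oral agent, this trial excludes screening glucose above 150 mg/dl where the source trials excluded 200 or more, and drug-related adverse events declined in the extension. No change to the sample size is needed. The reason to act is that the follow-up rule should be settled before an event occurs, so that retention of a primary value is not decided ad hoc.

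**What to change.** Reword the glucose bullet under Stopping rules to match Protection against risks and section K, for example:

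*If fasting plasma glucose is ≥200 mg/dl on two consecutive measures, study pills are permanently discontinued and the participant is referred to his/her physician. Scheduled measurements, including the day 361 D₃-creatine dose and the 12-month urine, continue unless consent is withdrawn or the PI judges continued measurement unsafe.*

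The cost is one reworded bullet. The threshold for stopping the drug is unchanged, physician referral and the PI's safety discretion are kept, and the visits and the second D₃-creatine dose are already scheduled.
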